4.5.2 Clinical Adverse Events

Treatment emergent AEs (TEAEs)

All AEs will be coded using the MedDRA dictionary version 23.0 or higher.

All AEs will be analyzed based on the principle of treatment emergence. A treatment emergent AE is defined as an AE that started or worsened after the start of first infusion of study treatment.

To define treatment emergence for AEs with missing start or stop date or time the following additional criteria will be used:

- if both the start and stop dates for a particular AE are missing, then that AE is considered treatment emergent.
- if the start date for a particular AE is missing and the stop date/time falls after the first dose date/time, then that AE is considered treatment emergent.
- if the start date for a particular AE was the same as the first dose date, and the start time was missing, then that event is considered treatment emergent.

For AEs with a partial start date, the year/month of the event date will be compared to that of the first dosing date to determine whether the event is treatment emergent.

In addition, SAEs that occurred since a subject was screened in the study and prior to the first infusion of study treatment, which by definition are not treatment emergent, will be analyzed separately.

Only TEAEs will be included in the AE tables, unless otherwise specified. Listings of AEs will include all events, whether treatment emergent or not.

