2.1.2 Years 2-4 (Active-Treatment Dose-Blinded Portion of the Study)

Prior to Infusion 14 (the first dose of Year 2) at Week 52, subjects who received placebo in Year 1 will be randomized into 1 of the active-dosing arms for Year 2; these subjects will receive BIIB054 in Year 2. Subjects who received BIIB054 (250mg, 1250 mg or 3500 mg) in Year 1 of the study will continue with the same dose regimen in Year 2. Subjects receiving the 250-mg dose in Year 1 continued on their original dose assignment.

CONFIDENTIAL

The information contained herein may not be used, disclosed, or published without the written consent of Biogen MA Inc.

	Statistical Analysis Plan Dose Blinded Extension Period	V2.0
---	--	-------------

Subjects will receive 12 additional doses of BIIB054 (250, 1250, or 3500 mg) in Year 2 and up to 16 additional doses in Years 3 and 4. Up until the last subject in the study has had his or her last dose in Year 2 of the study (Week 96 Visit), eligible subjects will be able to continue treatment once every 4 weeks.

[figure not shown]
Subjects who complete dosing through Week 96 and the Final Visit 12 weeks after the last visit will be considered Year 2 completers in the eCRF.

See Figure 2 for a depiction of the duration of dosing in Years 3 and 4 for subjects continuing dosing past Week 96.

Figure 4 in the protocol presents a flowchart for dosing and procedures from Week 96 through end of study, including how to determine which subjects are eligible to continue dosing past Week 96.

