For analyses on the DBE period or on the active treatment (placebo-controlled and DBE) period, DBE baseline will be used for delayed start subjects who are assigned to receiving BIIB054 in the DBE period. Change from baseline will be defined as post-baseline value minus baseline value.

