4.1.1 Analysis Population

- **Intent-to-treat (ITT) population:**
The Intent-to-treat population is defined as all randomized subjects who received at least one dose of study treatment (BIIB054 or placebo).
- **Safety population:**
The safety population is defined as all subjects who received at least one dose of study treatment (BIIB054 or placebo).
- **Pharmacodynamic analysis population:**
The pharmacodynamic population is defined as a subset of the ITT population with at least 1 post-baseline pharmacodynamic measurement.
- **PK analysis population:**
The PK population is defined as a subset of the ITT population who have at least 1 measurable BIIB054 concentration in serum [REDACTED]

[REDACTED]

- **Immunogenicity population:**
Immunogenicity analysis will be performed for all subjects in the safety population.

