4.1.2 Analyses period

Depending on the purpose, different analyses will be conducted on the following study periods:

1. DBE period. Only data in the DBE period will be included in these analyses. For example, incidence table of adverse events in the DBE period.
2. Placebo-controlled and DBE period. All the data in the placebo-controlled and DBE periods will be included in these analyses. For example, mean plot of actual laboratory values in the placebo-controlled and DBE period.

CONFIDENTIAL

The information contained herein may not be used, disclosed, or published without the written consent of Biogen MA Inc.

	Statistical Analysis Plan Dose Blinded Extension Period	V2.0
---	--	-------------

3. Active treatment (placebo-controlled and DBE) period (i.e., Total BIIB054 experience) period. Active treatment period is defined as the study period(s) that a subject is assigned to BIIB054. For early start subjects – subjects who are assigned to BIIB054 in both placebo-controlled and DBE period, all the data (placebo-controlled and DBE periods) will be included in the analyses. For delayed start subjects – subjects who are assigned to placebo in Year 1 and BIIB054 in the DBE period, only data in the DBE period will be included. For example, incidence table of adverse events in the active treatment (placebo-controlled and DBE) period will not include the AEs started on placebo treatment in year 1.

Subjects to be included in a certain output is determined by both the analysis population and the analysis period. For example, the incidence table of adverse events in the DBE period will include subjects in the safety population for the DBE period, i.e., all randomized subjects who received at least one dose of study treatment in the DBE period. The incidence table of adverse events in the active treatment (placebo-controlled and DBE) period will include subjects in the safety population for the active treatment period, i.e., all randomized subjects who received at least one dose of study treatment in the active treatment period. In this SAP we do not separately define the analysis population in each analysis period.

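### In the extension's active-treatment AE tables, an event that starts on placebo and worsens on BIIB054 drops out for delayed-start subjects, while comparable worsening counts for early-start subjects

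*SAP*

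**What the plan says.** All references are to the DBE SAP (V2.0) unless stated.

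- **Emergence (4.5.2).** "A treatment emergent AE is defined as an AE that started or worsened after the start of first infusion of study treatment". No separate version is given for the DBE period or the active-treatment period. The missing-date and partial-date rules in the same section also refer to the first dose.
- **Which events are tabulated (4.5.2).** "Only TEAEs will be included in the AE tables, unless otherwise specified".
- **Meaning of study treatment (4.1.1).** "The safety population is defined as all subjects who received at least one dose of study treatment (BIIB054 or placebo"), so placebo counts as study treatment.
- **Delayed start (2.1.2).** "subjects who received placebo in Year 1 will be randomized into 1 of the active-dosing arms for Year 2". The first BIIB054 infusion of these subjects is at Week 52.
- **Active-treatment period (4.1.2).** Delayed-start subjects contribute DBE data only. As the worked example for AEs, the incidence table for the "active treatment (placebo-controlled and DBE) period will not include the AEs started on placebo treatment in year 1".
- **Baseline (4.1).** For DBE-period and active-treatment analyses, "DBE baseline will be used for delayed start subjects who are assigned to receiving BIIB054 in the DBE period".
- **Follow-up time (4.5.1, 4.5.2.2).** For active-treatment incidence rates, delayed-start follow-up runs from the first DBE dose.

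**The concern.** The active-treatment period is meant to show all experience on BIIB054, and dose-related safety is a secondary objective. Its columns should therefore apply one definition of a BIIB054 event. They do not. Worsening after starting BIIB054 counts when the event predates an early-start subject's first infusion. It does not count when the event began during a delayed-start subject's placebo year.

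The active-treatment tables in 4.5.2.2 include severe AEs, SAEs, drug-related AEs and AEs leading to discontinuation or withdrawal. A mild placebo-onset event that became severe, or led to stopping, on BIIB054 could be missing from them. The error runs in one direction, towards fewer events in the delayed-start columns and in the BIIB054 total. The incidence-rate tables add a mismatch: the denominator starts at the first DBE dose, while the emergence rule behind the numerator starts at the first placebo infusion.

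**Working it through.** The plan gives no figure on this point, so the check applies its rules to cases.

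| Case | Emergent under 4.5.2? | Excluded under 4.1.2? | In active-treatment AE tables? |
|---|---|---|---|
| (a) Delayed start: AE starts on placebo, worsens after first BIIB054 infusion | Yes, counted from the placebo infusion | Yes, by onset | No |
| (b) Delayed start: AE starts in the DBE | Yes | No | Yes |
| (c) Delayed start: AE starts before the first placebo infusion, worsens only in the DBE | Yes | Not caught by the wording | Yes |
| (d) Early start: AE present before first BIIB054 infusion, worsens after it | Yes | Does not apply | Yes |

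Cases (a) and (d) share the feature that matters: the event was present before BIIB054 and became worse on it. They get opposite results. Cases (a) and (c) also differ, although both are delayed-start subjects who worsen on BIIB054.

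**Which rule removes the event.** The emergence anchor alone does not. It makes the event in case (a) treatment-emergent. The onset exclusion in 4.1.2 then removes it. Because emergence is never reset to the first BIIB054 infusion, no worsening rule brings it back. The defect lies in the two sections together.

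**What the SAP resets elsewhere.** Delayed-start subjects move to the DBE baseline under the general rule in 4.1. This is stated again for laboratory data (4.5.3), vital signs (4.5.4), ECG (4.5.5) and anti-drug antibodies (4.9.2). Follow-up time for AE rates is reset as well (4.5.1, 4.5.2.2). The emergence rule is not.

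**Missing dates.** An AE in a delayed-start subject with a missing start and a stop date in the DBE is emergent under 4.5.2, because it stops after the first dose. Nothing says whether its onset falls before or after the switch to BIIB054, so the onset exclusion cannot be applied to it consistently.

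**Share of subjects concerned.** Inputs are from Tables 3.2 and 3.3, assuming that everyone randomised is dosed and that the 10% planning dropout holds.

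- Delayed start: 101 × 0.9 ≈ 91
- Early start: 54 + 101 + 101 = 256
- Share of those exposed to BIIB054: 91 / (91 + 256) = 91 / 347 ≈ 26%

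**Illustration only.** Suppose 20–40% of delayed-start subjects have an ongoing AE at Week 52 and 5–15% of those worsen on BIIB054. Neither range comes from the document.

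- Low: 91 × 0.20 × 0.05 ≈ 0.9 subjects
- High: 91 × 0.40 × 0.15 ≈ 5.5 subjects
- Share of delayed start: 0.9/91 to 5.5/91, about 1% to 6%
- Share of all exposed: 0.9/347 to 5.5/347, about 0.3% to 1.6%

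**The case against.** The best defence is that the exclusion in 4.1.2 is only an example. The operative rule limits delayed-start subjects to DBE data, and a worsening dated in the DBE could be read as DBE data. Section 4.5.1 also treats the first dose, for active-treatment analyses, as the first one in the period when BIIB054 is first received. With the general baseline rule, that suggests where the anchor was meant to be. This shows intent but does not settle the text. The sentence in 4.5.1 defines follow-up time, not emergence, and the example in 4.1.2 is the only statement of how the period rule applies to AEs. It selects by onset.

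A second defence stands in part. If sites record worsening as a new AE with its own start date, the event starts in the DBE and is counted. The SAP states no such convention, and the word worsened in its definition suggests that worsening of an existing event was meant to matter.

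Three stronger readings are tempting and are not supported:

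- **That such an event never counts as a BIIB054 event.** The DBE-period tables (4.5.2.1) carry no onset exclusion, so a worsening in the DBE can enter them. Listings include all AEs.
- **That AEs alone keep the placebo anchor.** The C-SSRS (4.5.7) and MRI (4.5.8) sections also state no delayed-start baseline of their own.
- **That an event with a missing start and a Year 1 stop date distorts these tables.** The limit to DBE data keeps it out, whatever its emergence flag.

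**Conclusion.** The point holds for the active-treatment AE tables. As written, 4.5.2 and 4.1.2 together treat worsening on BIIB054 differently by column. The result is an undercount in the delayed-start columns and in the BIIB054 total, provided worsening is not recorded as a new AE.

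The size cannot be derived from the document. Delayed-start subjects are about a quarter of those exposed, but only those with a placebo-onset event that worsens are affected. The illustration of roughly 1 to 5 subjects rests wholly on assumed rates. Each subject counts once per category, so the effect on broad categories such as any AE may be smaller still. These tables are descriptive and the SAP specifies no hypothesis test for AEs. The case for correction is consistency and direction of error, with the greatest weight on severe events and events leading to discontinuation, where a single case can matter.

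**What to change.** 1. **Section 4.5.2.** Add that, for DBE-period and active-treatment tables, an AE in a delayed-start subject is treatment-emergent if it started, or worsened in severity, after the start of the first BIIB054 infusion. Use that infusion as the anchor for AEs with a missing or partial start date, unless the event is shown to have ended before it.
2. **Section 4.1.2.** Limit the exclusion to AEs that started on placebo and did not worsen after the first BIIB054 infusion.
3. **Second copy.** The DBE SAP appears twice in the file. Make the same changes in both copies.

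The cost is a few sentences and one derived flag. The condition is that worsening can be dated in the AE data, either as a new record or as a dated change in severity. If each AE holds only one onset date and its maximum severity, the flag cannot be derived from those fields. The SAP should therefore state which recording convention applies.

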4.5.2.1 Summary and incidence analysis

Overall summary of AE table will be done for the following periods, by DBE treatment groups:

- DBE period, and,

CONFIDENTIAL

The information contained herein may not be used, disclosed, or published without the written consent of Biogen MA Inc.

	Statistical Analysis Plan Dose Blinded Extension Period	V2.0
---	--	-------------

- the active treatment (placebo-controlled and DBE) period

The following information will be summarized: the number of subjects with any AE, with any AE by maximum severity, with any related AE (related to study drug as assessed by investigator), with radioligand rated AE, with SAE, with related SAE, with radioligand rated SAE, with AE leading to study drug discontinuation, with AE leading to study withdrawal and the number of deaths.

The sorting order of AE incidence tables, unless otherwise specified, will be by decreasing frequency order of “BIIB054 total” column within each category in the tables presented by DBE treatment group. A subject is counted only once within each category in each table. For example, for the table of AEs by system organ class and preferred terms sorted by decreasing frequency presented by DBE treatment group, system organ class will be presented in decreasing frequency order of BIIB054 total column, and within each system organ class, preferred terms will be presented in decreasing frequency order of BIIB054 total column. A subject is counted only once within each system organ class and preferred term.

The severity of AEs and SAEs is graded using the CTCAE grade, version 5.0. The categorisation of severity is as follows: grade 1 (mild), 2 (moderate), 3 (severe or medically significant), 4 (life-threatening) and 5 (death). Severe AEs and SAEs are classed as CTCAE grade ≥ 3 .

The following AE incidence tables will be provided for the DBE period:

1. AEs by system organ class and preferred term sorted by decreasing frequency
2. AEs by preferred term
3. Severe AEs by system organ class and preferred term
4. Severe AEs by preferred term
5. Study drug related AEs by system organ class and preferred term
6. SAEs by system organ class and preferred term sorted by decreasing frequency
7. SAEs by preferred term
8. Study drug related SAEs by system organ class and preferred term
9. AEs that led to discontinuation of study treatment by system organ class and preferred term
10. AEs that led to withdrawal from study by system organ class and preferred term

4.5.2.2 **Incidence and incidence rate analysis for active treatment (placebo-controlled and DBE) period**

Due to the different length of active treatment (placebo-controlled and DBE) period in early start versus delayed start subjects, both incidence (proportion) tables and incidence rate tables will be used for AE analyses in this period. The entire follow-up time is from the first dose in

CONFIDENTIAL

The information contained herein may not be used, disclosed, or published without the written consent of Biogen MA Inc.

	Statistical Analysis Plan Dose Blinded Extension Period	V2.0
---	--	-------------

active treatment period (first dose in placebo-controlled period for early start subjects and first dose in DBE period for delayed start subjects) until the last day in the study.

The following incidence (proportion) will be provided for the active treatment (placebo-controlled and DBE) period. The follow-up adjusted incidence rate table will be provided for 1, 10, 12, 14, 16 and 17.

1. AEs by system organ class and preferred term sorted by decreasing frequency
2. AEs by system organ class and preferred term sorted by alphabetical order analysis
3. AEs by system organ class
4. AEs by preferred term
5. AEs with an incidence of 5% or more in any treatment group by preferred term
6. Severe AEs by system organ class and preferred term
7. Severe AEs by preferred term
8. AEs by maximum severity by system organ class and preferred term (System organ class will be presented alphabetically. Preferred term will be presented in decreasing frequency order).
9. AEs by maximum severity by preferred term (Preferred term will be presented in decreasing frequency order)
10. Study drug related AEs by system organ class and preferred term
11. Radioligand related AEs by system organ class and preferred term
12. SAEs by system organ class and preferred term
13. SAEs by preferred term
14. Study drug related SAEs by system organ class and preferred term
15. Radioligand related SAEs by system organ class and preferred term
16. AEs that led to discontinuation of study treatment by system organ class and preferred term
17. AEs that led to withdrawal from study by system organ class and preferred term
18. AEs that occurred within 2 hours from infusion start by system organ class and preferred term

The following listings will be provided for the placebo-controlled and DBE period:

1. Listing of AEs
2. Listing of SAEs
3. Listing of AEs that led to discontinuation of study treatment
4. Listing of AEs that led to withdrawal from study
5. Listing of AEs that occurred within 2 hours from infusion start
6. Listing of study drug related AEs
7. Listing of radioligand related AEs

CONFIDENTIAL

The information contained herein may not be used, disclosed, or published without the written consent of Biogen MA Inc.

	Statistical Analysis Plan Dose Blinded Extension Period	V2.0
---	--	-------------

8. Listing of deaths

4.5.3 Clinical Laboratory Data

The following laboratory assessments will be performed in Year 2-4 to evaluate the safety profile of BIIB054:

- Hematology: Complete blood count with differential and platelet count, INR, PT, and APTT
- Blood chemistry: total protein, albumin, creatinine, blood urea nitrogen, uric acid, bilirubin (total and direct), alkaline phosphatase, alanine aminotransferase, aspartate aminotransferase, gamma-glutamyl transferase, glucose, calcium, phosphorus, bicarbonate, chloride, sodium, and potassium
- Urinalysis: dipstick for blood, protein, and glucose (microscopic examination may also be performed)

4.5.3.1 Quantitative analyses

For quantitative analyses, analysis period is active treatment (placebo-controlled and DBE) period. For numeric laboratory parameters, actual values will be summarized by visit for all the common visits in both Cohort A and B in the active treatment (placebo-controlled and DBE) period. Number of evaluable subjects, mean, standard deviation, median, 25% and 75% quartiles, minimum and maximum values will be presented at each visit. Plots of mean actual values (with standard error) for key numeric laboratory parameters at each visit for all the visits in the active treatment (placebo-controlled and DBE) period will be provided.

Plots of mean actual values (with standard error) for numeric laboratory parameters at each visit for all the visits in the active treatment (placebo-controlled and DBE) period may be provided.

Change from baseline and percent change from baseline for numeric laboratory parameters will be summarized in the active treatment (placebo-controlled and DBE) period. Placebo-controlled baseline will be used for early start subjects and DBE baseline will be used for delayed start subjects. Change and percent change from baseline will be calculated based on the DBE baseline for delayed start subjects. Number of evaluable subjects, mean, standard deviation, median, 25% and 75% quartiles, minimum and maximum values will be presented at each visit.

Listings of individual laboratory measurements by patients for all the parameters will be provided for placebo-controlled and DBE period.

CONFIDENTIAL

The information contained herein may not be used, disclosed, or published without the written consent of Biogen MA Inc.

	Statistical Analysis Plan Dose Blinded Extension Period	V2.0
---	--	-------------

Visit windows for by visit summaries

For laboratory by visit summaries, the analysis visit should be defined using visit windows (see Table 1 in the Appendix). Visit windows are generally from mid-points between the visit before to the current, and the midpoint from the current visit to the next visit. If there is more than 1 value in the same analysis visit window for a certain parameter for a subject, then the closest record to the target visit day will be used for the by visit analysis. If there are 2 values in the same analysis visit window with the same distance from the target visit day for a certain parameter for a subject, then the record with the later date will be used for the by visit analysis. If there are 2 values on the same day for a certain parameter for a subject, then the record with the later time will be used for the by visit analysis.

4.5.3.2 **Qualitative analyses**

For qualitative analyses, all available values will be included (not just the “analyzed record” within each visit window in the quantitative analyses). Analysis period is active treatment (placebo-controlled and DBE) period.

Shift analyses

Laboratory data will be summarized using shift tables where appropriate for the active treatment (placebo-controlled and DBE) period. Each subject’s hematology, blood chemistry and urinalysis numeric values will be flagged as “low”, “normal”, or “high” relative to the normal ranges of the central laboratory or as “unknown” if no result is available. Each subject’s urinalysis categorical values will be flagged as “positive” or “negative”, or “unknown” if no value is available.

Shifts from baseline to high/low status will be presented for hematology, blood chemistry and urinalysis numeric parameters, and shifts from baseline to abnormal (positive) will be presented for urinalysis categorical parameters. Shift to low includes normal to low, high to low, and unknown to low; Shift to high includes normal to high, low to high, and unknown to high. Subjects need to have at least one post-baseline evaluation and a baseline value not low or high or positive (including missing) in order to be included in the analysis.

For early start subjects, the placebo-controlled baseline will be used and shifts that occurred in either placebo-controlled or DBE period will be included. For delayed start subjects, the DBE baseline will be used and shifts that occurred in the DBE period based on DBE baseline will be included.

Potentially Clinically Significant (PCS) laboratory abnormalities analyses

Please refer to the placebo-controlled SAP for the parameters and criteria for potentially clinically significant laboratory abnormalities analyses.

The number of subjects with potentially clinically significant laboratory abnormalities post-baseline will be summarized for the active treatment (placebo-controlled and DBE) period.

CONFIDENTIAL

The information contained herein may not be used, disclosed, or published without the written consent of Biogen MA Inc.

	Statistical Analysis Plan Dose Blinded Extension Period	V2.0
---	--	-------------

Subjects need to have at least one post-baseline evaluation in the active treatment period in order to be included in the analysis. For early start subjects, the placebo-controlled baseline will be used and abnormalities that occurred in either placebo-controlled or DBE period will be included. For delayed start subjects, the DBE baseline will be used and PCS abnormalities that occurred in the DBE period based on DBE baseline will be included.

A listing of subjects with PCS laboratory abnormalities in the active treatment (placebo-controlled and DBE) period will also be provided, with all the data in the placebo-controlled and DBE period will be listed.

Potential serious hepatotoxicity

Potential serious hepatotoxicity is defined as ALT or AST > 3x ULN and total bilirubin > 2x ULN at any time post-baseline, not necessarily concurrent, in the active treatment (placebo-controlled and DBE) period. A scatterplot of the maximum post-baseline ALT or AST value relative to ULN and maximum post-baseline total bilirubin value relative to ULN (not necessarily concurrent) will be provided. In addition, a line plot of ALT, AST, ALP and total bilirubin values over time for each subject with potential serious hepatotoxicity will be provided.

A listing of subjects with potential serious hepatotoxicity in the active treatment (placebo-controlled and DBE) period will be provided with the concurrent records labeled. All the data in the placebo-controlled and DBE period will be listed. Concurrent is defined as on the same day. Subjects with ALT > 1x ULN, > 3x ULN, > 5x ULN, > 10x ULN or > 20x ULN, subjects with AST > 1x ULN, > 3x ULN, > 5x ULN, > 10x ULN or > 20x ULN, subjects with total bilirubin > 1x ULN, > 1.5x ULN or > 2x ULN, subjects with ALP > 1x ULN or > 1.5x ULN, and subjects with AST or ALT > 3x ULN post-baseline accompanied by concurrently elevated total bilirubin > 1.5x ULN or > 2x ULN will be labeled.

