5.4.3.2 Qualitative laboratory analyses

For all qualitative analyses, all values will be included (not just the “analyzed record” within each visit window in the quantitative analyses).

Shift analyses

Laboratory data will be summarized using shift tables where appropriate. Each subject’s hematology, blood chemistry and urinalysis numeric values will be flagged as “low”, “normal”, or “high” relative to the normal ranges of the central laboratory or as “unknown” if no result is available. Each subject’s urinalysis categorical values will be flagged as “positive”, “negative”, or “unknown” if no value is available. Shifts from baseline to high/low status will be presented for hematology, blood chemistry and urinalysis numeric parameters, and shifts from baseline to abnormal (positive) will be presented for urinalysis categorical parameters.

In the hematology, blood chemistry and urinalysis numeric values shift summary tables, entries are numbers of subjects shift to low (or high) divided by number of subjects at risk

CONFIDENTIAL

The information contained herein may not be used, disclosed, or published without the written consent of Biogen MA Inc.

followed by corresponding percentages. Number at risk for shifting to low (or high) is the number of subjects whose baseline value was not low (or high) and who had at least one post-baseline evaluation. Shift to low includes normal to low, high to low, and unknown to low. Shift to high includes normal to high, low to high, and unknown to high.

In the urinalysis categorical values shift summary table, entries are numbers of subjects shift to abnormal (positive) divided by number of subjects at risk followed by corresponding percentages. Number at risk for shift to abnormal (positive) is the number of subjects whose baseline value was not abnormal (positive) and who had at least one post-baseline evaluation. Shift to abnormal (positive) includes normal or negative to positive and unknown to positive.

Potentially Clinically Significant (PCS) laboratory abnormalities analyses

For hematology, blood chemistry and urinalysis, the number of subjects with potentially clinically significant laboratory abnormalities post-baseline will be summarized for the parameters provided in [Table 5.1](#). Subjects need to have at least one post-baseline evaluation in order to be included in the analysis.

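### Read literally, the extension's inclusion rule for laboratory shift tables excludes the high-to-low and low-to-high shifts it has just defined, and shrinks the denominator relative to Year 1

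*SAP*

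**What the plan says.** The DBE SAP, section 4.5.3.2 (Shift analyses), flags each numeric haematology, chemistry and urinalysis value as low, normal, high or unknown, and each categorical urinalysis value as positive, negative or unknown. It then defines the events: "Shift to low includes normal to low, high to low, and unknown to low", with the mirror definition for shift to high. The sentence that follows sets who is analysed. A subject needs at least one post-baseline evaluation and "a baseline value not low or high or positive (including missing) in order to be included in the analysis".

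The Year 1 SAP, section 5.4.3.2, defines the same events but sets the risk set by direction: "Number at risk for shifting to low (or high) is the number of subjects whose baseline value was not low (or high"), again with at least one post-baseline evaluation. For categorical urinalysis it requires a baseline that is not positive.

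The DBE shift text does not refer back to the Year 1 shift rule. The part on potentially clinically significant (PCS) abnormalities that follows it does refer to the placebo-controlled SAP for its criteria. The DBE SAP is reproduced twice in the file, and the wording is identical in both copies.

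**The concern.** Two adjacent sentences appear to conflict. The first makes a high baseline a valid origin for a shift to low. The second, read as one joint condition, removes any subject whose baseline is high. The same holds for low baselines and shifts to high.

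If the rule is programmed as written, two of the defined shifts cannot occur in the table. In addition, every numeric parameter gets a denominator that leaves out both low and high baselines, where Year 1 leaves out only the one matching the direction of shift. For early-start subjects the integrated table uses the Year 1 baseline and includes Year 1 shifts. One study would therefore report shift percentages under two different risk-set rules without saying so.

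**Working it through.** The plan states no figure to reproduce. The check has two parts: a comparison of baseline categories, and an illustration of size.

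**1. Categories, numeric parameters**

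| Direction | Origins listed as shifts (both SAPs) | Admitted, Year 1 rule | Admitted, DBE rule read literally | Listed but not admitted by DBE |
|---|---|---|---|---|
| To low | normal, high, unknown | normal, high, unknown | normal, unknown | high |
| To high | normal, low, unknown | normal, low, unknown | normal, unknown | low |

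Under the Year 1 rule the admitted baselines equal the listed origins exactly. Under the literal DBE rule one listed origin is missing in each direction. For categorical urinalysis both SAPs require a baseline that is not positive, so they agree.

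**2. Denominators in one arm**

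Input from the DBE SAP, Table 3.2: 101 subjects in the 1250 mg arm, and the same number in the 3500 mg arm. The baseline shares are assumptions. With L low and H high at baseline, the Year 1 denominators are 101 − L (to low) and 101 − H (to high); the literal DBE denominator is 101 − L − H for both.

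| Assumed low / high | Year 1, to low | Year 1, to high | DBE literal, both |
|---|---|---|---|
| 2% / 2% | 99 | 99 | 97 |
| 5% / 5% | 96 | 96 | 91 |
| 5% / 10% | 96 | 91 | 86 |
| 10% / 20% | 91 | 81 | 71 |

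**3. Effect on a rate**

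Early-start subjects from the same table: 54 + 101 + 101 = 256. Assumed: 2.5% low at baseline, and 10 shifts to low, all from normal or unknown baselines.

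- Year 1 rule: 256 × 0.975 = 249.6, about 250; 10/250 = 4.0%.
- DBE literal, 2.5% high: 256 × 0.950 = 243.2, about 243; 10/243 = 4.1%.
- DBE literal, 10% high: 256 × 0.875 = 224; 10/224 = 4.5%.
- DBE literal, 20% high: 256 × 0.775 = 198.4, about 198; 10/198 = 5.1% (5.0% without rounding the denominator).
- DBE literal, 30% high: 256 × 0.675 = 172.8, about 173; 10/173 = 5.8%.

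The direction is not fixed. If one of the 10 shifts came from a high baseline, the literal rule would drop it. With 2.5% high, the rate would be 9/243 = 3.7%, below the Year 1 figure of 4.0%.

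**The case against.** The strongest defence is that the sentence is compressed, not wrong. It closes a paragraph covering three tables (to low, to high, to positive) and names three baseline states. A numeric value cannot be positive under the SAP's own flags, so the list must be distributed at least in part: not low for the first table, not high for the second, not positive for the third. The allowance for missing baselines then matches the unknown-to-low and unknown-to-high origins, and the rule agrees with Year 1. The preceding sentence, which names the opposite-direction shifts, supports this reading. The Year 1 SAP compresses its own rule in a similar way.

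This reading is plausible and may be what was meant. However, the sentence has no *respectively*, no pairing of direction with baseline, and no reference back to Year 1. The Year 1 text does tie each direction to its own risk set. A stated inclusion rule should not need interpretation to avoid cancelling the definition before it.

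Several stronger inferences are tempting, and the documents do not support them:

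- **That shifts will certainly be lost.** This depends on the literal reading being programmed.
- **That reversals would enter the numerator without being in the denominator.** The sentence governs inclusion in the analysis as a whole, so an excluded subject contributes to neither.
- **That the largest swings would disappear from the report.** Section 4.5.3.1 lists individual values for all parameters, and the PCS count in section 4.5.3.2 does not exclude subjects by baseline status.
- **That delayed-start subjects would be affected differently.** They use the DBE baseline by design, and would do so under the Year 1 rule too. Nothing in the documents shows a differential loss.

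**Conclusion.** The point holds as a defect of wording with a conditional consequence. Read literally, the DBE inclusion sentence contradicts the shift definition before it and departs from the Year 1 at-risk rule. Read as shorthand, it agrees with both. The text does not settle which is meant.

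The reach is limited to descriptive shift tables for numeric parameters in the active treatment period. Categorical urinalysis is unaffected, and no efficacy conclusion depends on it.

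The size cannot be fixed from the documents, because they give no baseline abnormality rates. It is small when few subjects are abnormal in the opposite direction: 4.0% against 4.1% at an assumed 2.5%. A reader might take the 5.8% at the top of the range, about 1.4 times the Year 1 figure, as the expected distortion. It rests on an assumed 30% high at baseline and on no shift coming from a high baseline, and should not be quoted as typical. This is a desirable correction, not an essential one.

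**What to change.** In the DBE SAP, section 4.5.3.2, replace the inclusion sentence with the Year 1 rule, stated by direction:

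- For shift to low, the number at risk is subjects whose baseline is not low, including unknown, with at least one post-baseline value in the active treatment period.
- For shift to high, it is subjects whose baseline is not high, including unknown, with at least one such value.
- For shift to positive (categorical urinalysis), it is subjects whose baseline is not positive, including unknown, with at least one such value.

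If the shorthand was intended, this only states it. The cost is one sentence. The Year 1 risk-set logic can be reused with the baselines the DBE SAP already assigns to early-start and delayed-start subjects.
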